5.1.3 Main Definitions and criteria for evaluating efficacy and safety

Efficacy will be evaluated using the success rate of appropriate shocks. In order for a shock to be appropriate, it must be administered while a patient is experiencing either sustained VT or VF. Otherwise, the shock is inappropriate.

The risk associated with the use of LifeVest will be assessed in terms of inappropriate shocks. Any shock administered to a patient who is not experiencing either VF or sustained VT at the time of administration is an Inappropriate Shock. Even if the patient experiences VT or VF and the condition resolves by itself or bystanders intervention just prior to administration of the shock, it would be classified as Inappropriate.

The classification of individual shocks into the categories of Appropriate and Inappropriate is quite unambiguous, so long as the ECG signal is of sufficient strength to be able to accurately determine the heart rhythm. If the signal is obscured by noise and it is not possible to unambiguously determine the rhythm the shock is generally categorized as Inappropriate, because the noise is generally the cause of the false detection.

All appropriate and inappropriate WCD shock deliveries, as well as VT/VF events will be recorded and analyzed by means of precise ECG recording, provided the VT/VF exceeds the programmed rate threshold for event detection by the WCD. ECG recordings are retrievable from a central server to which all WCD data and ECGs will be transmitted automatically. Similarly, all shock-withhold VT/VF events or VT/VF events that terminated spontaneously will be recorded and counted. All potential bradyarrhythmic or asystole events will be recorded. The device is programmed to record events which are slower than 20 beats per minute or have a QRS amplitude less than 200 microvolts (peak to peak), provided the patient does not respond to alarms.

There will be assessment of all ventricular tachyarrhythmic events, either treated by WCD-shock or with shock withheld by the patient. Furthermore, the assessment of the overall outcome (death) and of clinical events (cardiac and non-cardiac), such as hospitalization, heart failure status, ischemic events, ICD implantation, Pacemaker implantation, surgical interventions (CABG or valve replacement) during the period of WCD wearing.

The assessment and classification of the type of arrhythmic events will be carried out by an independent Clinical Event Committee (CEC) by evaluating the ECG data provided by the WCD during wearing and recorded on the central ECG and WCD data server. Members of the CEC are listed in Appendix A. Events will be separately reviewed by at least two CEC members. A third reviewer will review events for which there is not agreement between the first two reviews.

Primary parameters to be assessed during follow-up:

1. *Arrhythmic (VT/VF) events and type of event*
2. *Appropriateness of shock delivery*
3. *All-cause mortality*

4. *Hospitalization*
5. *Cardiac events*
6. *Non-cardiac events (e.g. stroke, renal failure)*

Secondary parameters to be assessed:

1. *Analysis of primary outcome parameters (see above) in sub-groups according to their clinical profile at baseline (age, gender, disease etiology, type of inherited arrhythmia syndrome, etc.)*
2. *LV-EF at time of WCD end of use*
3. *Type and character of arrhythmic events*
4. *Type and character of cardiac events*

5.1.4 Methods and timing for assessing, recording, and analysing variables.

During wearing of the WCD the responsible physician in the participating centers is able to check the event history, appropriate use of the WCD, compliance of the patient and potential complications of the WCD by means of a password protected access to the central server. The patient's ECGs in case of detection of arrhythmias and all wearing data are automatically transmitted from the WCD to the server. After an arrhythmic event, the patient is instructed to inform not only the emergency ambulance but also the responsible physician and the ZOLL Company about the event. The responsible physician is able to analyze the event and will document all available data in the e-CRF system. The ECG recording during the event is also stored and retrievable from the server.

All arrhythmia and clinical events as well as the clinical status (including measurement of LV-EF) of the patient during the WCD wearing period are documented in the e-CRF by the responsible physician. All arrhythmia episodes detected by the WCD will be reviewed and evaluated by an independent Clinical Event Committee. All patient data from France post marketing study will be gathered by CRI on e-CRFs.

After the first month of use, all participating patients will be surveyed confidentially to assess their quality of life related to their health status and use of the WCD. Because patients who are prescribed a LifeVest are typically in an acute episode of care involving a hospitalization (e.g., ICD explant procedure due to infection, post-MI, etc.), the Science Committee felt that a general population QoL survey, such as the SF-12 or EQ5D would not be as useful in this study. Other more relevant QoL instruments that have been validated are generally condition-specific are not applicable across the entire study population. Therefore, a patient survey developed specifically for LifeVest patients will be used for this study. This instrument has been used in published, peer reviewed research.¹⁶ Specific detail on survey content can be found in Section 6.2 of the analysis description. Study coordinators will administer the survey. Patients who have not responded to the initial survey request will be reminded to participate approximately seven days after the initial invitation.

5.1.5 Any procedures for the replacement of subjects.

The investigator is encouraged to try to enrol all patients to whom the WCD has been prescribed (provided informed consent is given by the patient). This includes also those patients who have already com-

pleted use of LifeVest before start of the study in the corresponding study site. No replacement of patients is planned because of the observational nature of the study.

5.2 Subjects

Study population will consist of patients at high risk for SCD and receiving LifeVest as a bridge therapy to heart transplantation, to ICD or to improvement of LV function.

5.2.1 Inclusion criteria for subject selection.

- Patients receiving a LifeVest prescription in clinical routine for the following indications:
 - a) implantable cardiac defibrillator (ICD) removal due to cardiac device infections,
 - b) a bridge to heart transplantation,
 - c) in the early post-MI period with left ventricular (LV) dysfunction (LVEF <30%),
 - d) a recent coronary revascularization with LV dysfunction (LVEF < 30%).
- Patients who have given their consent to participate.

This includes also those patients who have already completed use of LifeVest before start of the study in the corresponding study site (retrospective inclusion).

5.2.2 Exclusion criteria for subject selection.

There are no exclusion criteria for this study other than if the patient does not provide informed consent to participate. All patients prescribed a LifeVest will be invited to participate. All patients that were previously prescribed a LifeVest before the start of this study will also be invited to participate by allowing access to their retrospective medical information.

5.2.3 Criteria and procedures for subject withdrawal or discontinuation.

A low rate of lost-to-follow up is expected since the LifeVest is rented to patients and should be returned to ZOLL by the end of the prescription. In case a patient is lost to follow up, the CepiDC a French database for automated coding of causes of death, will be interrogated to report if the patient is dead or alive, and if dead the cause of death.

All patients enrolled into the study can withdraw at any time regardless of the reason. Patients may withdraw consent for use of data and exit the study at any time without prejudice to further treatment.

Patients who have given consent to participate in the study but had the WCD for less than 8 days will be evaluated separately, but not withdrawn.

5.2.4 Participating centers and point of enrolment:

Participating centers: The study will start along with the early-stage marketing of LifeVest. All approved ICD implant centers in France, who are using LifeVest in their routine practice, will be invited to participate to the study. A registry will be created to collect geographic information and type of centers (public/private) refusing to participate. The reason for refusal will be reported in the registry. This registry will

be maintained by ClinSearch. Approved ICD implant centers in France who are not using LifeVest in their routine practice will be documented in the registry by ZOLL.

Participating patients: All patients in participating centers receiving LifeVest, satisfying the inclusion and exclusion criteria and consenting to participate will be consecutively included in the study. ZOLL will maintain a registry of all patients screened but not included in the study, to verify the representativeness of patients by the end of the study. It will be listed in this registry all patients meeting the selection criteria and having received a LifeVest. Demographics, indication and the reason for non-inclusion will be collected.

Start of documentation is at the time when the patient signs and dates the informed consent form. Data from medical history will be documented.

5.2.5 Personal Data and Data Protection

All data obtained in the context of the observational study are subject to data protection. This applies to patients' data as well as to investigators' personal data which may be included in any database of the sponsor or the CRO.

The investigating physicians shall take care that patient documents (e.g. copies of reports on special findings) transmitted to the CRO or the sponsor contain no names, but only the year of birth and a relevant patient study number. The storage of data for statistical analysis shall likewise be performed only under the patient's study number.

5.2.6 Data Handling and Record Keeping

a) *Completion of Case Report Forms*

All medical data in this observational study are to be recorded directly in the e-CRFs. Documentation on paper will be restricted to exceptional circumstances only.

The investigator must ensure the accuracy, completeness and timeliness (and legibility in case of documentation on paper) of data.

b) *Archiving*

The investigator must maintain confidential all study documentation, and take measures to prevent accidental or premature destruction of these documents. The investigator has to retain the study documents (i.e. investigator site file) after the completion or discontinuation of the study for the time period as required by national legislation. This especially applies to patients' signed informed consent forms and the patient identification list. The patient identification list will be destroyed at the end of the archiving period which is mandatory by national law as stated above.

The investigator must notify the sponsor prior to destroying any essential study documents within the specified period following completion or discontinuation of the study.

c) *Confidentiality*

All information disclosed or provided by the sponsor (or any company / institution acting on his behalf), or produced during the study, including, but not limited to, the clinical study protocol, the e-CRFs and the results obtained during the course of the study, is confidential. The investigator or any person under his/her authority agrees to undertake to keep confidential and not to disclose the information to any third party without prior written approval of the sponsor. The sub-investigators shall be bound by the same obligation as the investigator. The investigator shall in-

form the sub-investigators of the confidential nature of the study. Both, the investigator and the sub-investigators shall use the information solely for the purposes of the study, to the exclusion of any use for their own or for a third party's account.

5.2.7 Total expected duration of the clinical investigation:

The patient recruitment period will start along with the early-stage marketing of LifeVest. The inclusions will last for 2 years. The whole study duration will be of 24 months. Collected data will be analyzed and made available for the reimbursement dossier renewal (before April 2019). And final results will be submitted by the end of the study.

5.3.1.1 Informed Consent

Before entering data into the clinical study, each patient shall be informed about the use of their data in the clinical study according to the requirements of data privacy regulations, i.e. consent to processing medical data of the patient to a central scientific database. Sufficient time will be allowed for the infor-

mation to be read and for questions to be asked. The patient must be told that withdrawal of informed consent to use their data in the clinical study is possible at any time, without stating a reason and without prejudice, and does not cause any disadvantages.

5.3.1.2 Medical History

- Baseline demographic data
- Medical history of:
 - Coronary artery disease (CAD)
 - Myocardial infarction
 - PCI
 - CABG
 - Dilated Cardiomyopathy
 - Hypertrophic Cardiomyopathy
 - Heart Failure (NYHA II-IV)
 - Hospitalization for congestive heart failure
 - Cardiac arrest (CA)
 - Valve disease (aortic and mitral)
 - Stroke
 - Syncope
 - Atrial Fibrillation (A-Fib)
 - Inherited Arrhythmia Syndrome
 - Pacemaker Implantation
 - ICD Implantation
 - Congenital Heart Disease
 - Renal Disease

5.3.1.3 Symptoms and current status

- Comorbidities
- Concomitant treatments
- Physical examination
- Current cardiovascular symptoms
- Estimation of the degree of heart failure (NYHA Class I-IV)
- LV-EF at time of enrolment
- Indication for LifeVest and duration of prescription

5.3.1.4 At LifeVest end of use

- The reason for end of use (death, ICD implantation, heart transplantation, LV function improvement, patient's wish, etc)
- Reports on serious adverse events since the inclusion (ie: cardiac and non-cardiac death, hospitalization, heart surgery/revascularization, arrhythmic events and other cardiac events)

5.3.1.5 Data extracted from the LifeVest Network

- Wear time (hours per day)
- Description of all delivered treatments and associated ECG
- Description of asystole, detected arrhythmia with no treatment (e.g., short run of VT) and associated ECGs
- Information about any technical malfunctions and misuses, if applicable

5.3.1.6 Clinical Laboratory Tests

Only data of laboratory tests will be documented that have been performed as routine procedures according to clinical routine indications. All laboratory tests will be performed independently from participation in the France post marketing study.

5.3.2 Description of activities performed by sponsor representatives (excluding monitoring)

Personnel of the ZOLL company will instruct and train the patients in the correct use of the WCD. ZOLL personnel are continuously controlling the correct use and function of the WCD during WCD wearing time. They automatically replace the WCD in case of technical problems with the device. These activities by ZOLL company personnel are part of their routine obligations accompanying the use of the WCD (LifeVest ®), and are independent of this study.

5.3.3 Any known or foreseeable factors that may compromise the outcome of the clinical investigation or the interpretation of results

Only patients will receive the WCD if they are considered by their physician to be able to handle and use the WCD correctly.

5.4 Monitoring plan

Authorized, qualified representatives of the sponsor will accomplish on-site monitoring during the study. The accuracy and completeness of core CRF data of a sufficient number of patients will be checked on site against source documents. Details will be given in a risk based monitoring plan.

Quality management will assure that medical data are subject of continuous plausibility checks and data cleaning. The primary outcome parameters consist of follow-up and arrhythmic event raw data which are directly transmitted in clinical routine from the WCD device to a central database to which the treating physician has access via an internet platform enabling him to review any potential arrhythmic event

detected by the device. These data are not modified by human interactions, thus being *per se* valid and do not require source data verification.

6. Statistical considerations and methods

This is a nonrandomized, multicenter observational study. All consecutive LifeVest patients will be asked to participate. Demographic data will be reported on all consenting patients. Thus, all patients in this study will receive LifeVest treatment. Descriptive statistics will be used to report major clinical characteristics of consenting patients, and incidence and frequency of appropriate and inappropriate shocks.

For the overall survival rate calculation, the population of reference will correspond to the total number of patients enrolled who were prescribed the LifeVest.

Standard methods will be used to calculate adjusted survival rates. Kaplan Meier survival curves will be used to report total mortality and wear time. The time to event and census are defined here after.

All reasons for therapy discontinuation will be reported in tabular form.

Event	Decision	Event date or census date
Occurrence of the event	Not censored	Date of the event occurrence
No event and patient followed until the study end	Censored	Date of WCD withdrawal
Lost-to-follow-up	Censored	Date of the last visit or last contact

It is common to use a significance threshold of 5%. This will be applied in this study.

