Between August 2016 and April 2018, 1,110 patients were expected to receive LifeVest in clinical routine. Considering a participation rate of 50 % related to centers participating in the study and consent given, around 550 patients were considered to participate in this study.

Due to an observed recruitment rate exceeding the initial expectations, the recruitment goal was reached prematurely with an estimated enrollment of about 1,200 patients until 31st March 2018. After the end of recruitment, follow-up of patients is planned until 31st march 2019 (LPLV).

According to most recent data from literature, the frequency of ventricular tachyarrhythmic events with shock delivery within the spectrum of indications for the LifeVest device and within the associated wearing periods was estimated between 1% and 5% [6]. In this present study, a population of 550 patients was expected as primary assumption, allowing to observe a shock delivery rate ranging between 1%-5% with an absolute precision below 2% (0.8 for 1% and 1.8 for 5%). This sample size was considered to be statistically sufficient to answer the pre-defined research questions, however, the expected final population in the study of about 1,200 patients will increase the level of precision.

6. Analysis populations

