9.2 Follow-up data (wearing period) of ITT population

The following follow-up data will be described:

- Serious adverse events since inclusion by number of events in groups of
 - Type of event
 - Cardiac arrhythmic
 - Cardiac non-arrhythmic
 - Vascular non-cardiac (including stroke)
 - Cardiovascular without clearly defined other cause
 - Non-cardiovascular
 - Related hospital stay/prolongation of existing hospital stay
 - Causal relationship to WCD
 - Intensity
 - Outcome
 - Criteria for seriousness
- Time to first hospitalization
- Death
 - Cardiovascular
 - Cardiac
 - Vascular non-cardiac (including stroke)
 - Cardiovascular without clearly defined other cause
 - Non-cardiovascular
 - Death during prescription duration
 - Death while wearing the WCD
 - Death related to arrhythmic event
 - Death related to WCD dysfunction
- WCD events

WCD events/patients with WCD events with following event parameters:

- Type of event
- Termination of event
- Response button pressed
- Shock delivered
- Shock appropriate/inappropriate
- Occurrence of technical and non-technical problems during the wearing period
- Return of WCD device (end of therapy) due to:
 - Death
 - ICD implantation
 - Heart transplantation

- LV function improvement
- Patient's wish
- Other reason
- Clinical status on WCD return: Most recent LV-EF value, NYHA classification, risk assessment and if patient is still listed for heart transplantation
- Planned therapy after wearing period:
 - ICD implantation
 - PCI (Angioplasty, Stent)
 - Bypass surgery
 - Implantation of cardiac pacemaker
 - Heart transplantation
 - Implantation LVAD (left ventricular assist device)
 - Therapy with anti-arrhythmic agents
 - Other planned cardiac therapy
- Medication on WCD return

10. Primary analysis on ITT population

1. **Appropriate shocks** as measured by shocks delivered for adjudicated sustained ventricular tachycardia (VT) or ventricular fibrillation (VF) episodes.

- Quantitative analysis of appropriate shocks
- Analysis of the risk of not receiving appropriate shocks when necessary, calculated as number of non-terminated VT/VF events without shock delivery and without response button pressed/ number of VT/VF events

2. **Inappropriate shocks** as measured by shocks delivered for all episodes that are not adjudicated as sustained VT or VF episodes.

- Quantitative analysis of inappropriate shocks

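### The mortality Kaplan-Meier table sets no end date for deaths but censors survivors at WCD withdrawal or last contact, so any later death that reaches the data biases the curve upward

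*Combined protocol and SAP*

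**What the plan says.** Protocol section 6 states that "Kaplan Meier survival curves will be used to report total mortality and wear time" and then gives the only event and censoring rule in either document:

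- Event occurred: not censored, dated "Date of the event occurrence". No upper limit is attached to that date.
- "No event and patient followed until the study end": censored at "Date of WCD withdrawal".
- Lost to follow-up: censored at "Date of the last visit or last contact".

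SAP 11 plans Kaplan-Meier curves and Cox models for survival, by indication, medical history and disease etiology. It restates neither the event window nor the censoring dates, so the protocol table stands.

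For a patient lost to follow-up, protocol 5.2.3 says that the CepiDC cause-of-death database "will be interrogated to report if the patient is dead or alive". No time window is given for the lookup.

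**The concern.** The end of observation differs by outcome. A patient known to have died after withdrawal or last contact can contribute time up to the death. A patient known to be alive just as long afterwards contributes time only to withdrawal or last contact. Time after those dates is then counted only for people who die. The risk set late in the curve is small and enriched with future deaths, so each late death produces a large step.

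The lost-to-follow-up row shows this most plainly. One database query is made. If it returns a death, the first row can apply at the date of death. If it returns alive, the third row still censors at last contact.

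The curve and the Cox models would then not estimate mortality during WCD use. Protocol 5.1.1 expects wearing time to differ by indication, so the distortion could also differ between the indication groups that SAP 11 analyses. No subgroup calculation was made, so that last point is a possibility only. The results are meant for a reimbursement dossier.

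**Working it through.** **The plan's own figures.** The documents state no mortality rate, expected number of deaths or survival precision. The only design figure is the shock-rate precision at n = 550. With 1.96·√(p(1−p)/n) it reproduces: 0.83 points at 1% and 1.82 points at 5%, against the stated 0.8 and 1.8. It does not bear on this point.

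**Inputs.** From the documents: N about 1,200 (SAP 5) and mean participation of about 3 months (protocol 5.2.8). Assumed, because the documents are silent: exponential time on the WCD, death hazard h of 0.3% or 1% per month (the same on and off the device), 2%, 5% or 10% lost at a random point during wear, and CepiDC deaths found to month 12.

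**Step 1: weight of one late death.** Leaving deaths aside, the number still at risk at month m is 1,200·exp(−m/3).
- Month 6: 1,200·e^(−2) = 162, so one death moves the curve by 100/162 = 0.62 points.
- Month 9: 1,200·e^(−3) = 60, so one death moves it by 1.67 points.
- If all 1,200 stayed in the risk set, the step would be 100/1,200 = 0.08 points.

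**Step 2: extra deaths through CepiDC.** With 5% lost there are 60 lost patients, with last contact at about 1.5 months on average. At 1% per month, deaths from then to month 12 number about 60·(e^(−0.015) − e^(−0.12)) = 60·0.098 = 5.9. The simulation gave 5.95.

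**Step 3: effect through CepiDC alone.** Simulated mortality, with everyone censored at withdrawal or last contact, then with the table as written:

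| Hazard | Lost | 6 months | 9 months |
|---|---|---|---|
| 0.3%/month | 2% | 1.80% → 1.90% | 2.67% → 3.03% |
| 0.3%/month | 5% | 1.78% → 2.02% | 2.65% → 3.42% |
| 1%/month | 2% | 5.82% → 6.10% | 8.64% → 9.56% |
| 1%/month | 5% | 5.86% → 6.59% | 8.61% → 10.96% |
| 1%/month | 10% | 5.74% → 7.21% | 8.55% → 13.13% |

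Separate runs at 1% per month used a fixed prescription mix (1, 3 and 6 months in 20%, 55% and 25%, with 25% stopping early). With 2-5% lost they gave 6-month shifts between about 0.1 and 0.7 points.

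**Step 4: standard error.** Under exponential wear, Greenwood's formula gives SE = e^(−hm)·√[(h/N)(e^(km) − 1)/k], with k = h + 1/3. At h = 0.01:
- 6 months: 0.942·√[(0.01/1,200)·6.85/0.343] = 0.012, or 1.2 points.
- 9 months: 0.914·√[(0.01/1,200)·20.98/0.343] = 0.021, or 2.1 points.

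**Step 5: the routes that are not established.** Under the fixed prescription mix at 1% per month, true 6-month mortality is 5.8%. The table as written gives 6.7-7.0% if every death to the end of prescription is captured, 7.9-8.4% if a quarter of all deaths to March 2019 are, and about 12% if all are.

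**Step 6: direction.** Across 36 scenarios (two wear distributions, two hazards, a post-withdrawal hazard ratio of 0.5, 1 or 2, and 10%, 50% or 100% of later deaths recorded), the table gave higher 6- and 9-month mortality than uniform censoring at withdrawal every time. With no later deaths recorded, the two rules coincide.

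**The case against.** The strongest reply is that data collection stops at withdrawal, so there are no later deaths to count. Protocol 5.2.8 ends participation at withdrawal. Protocol 5.1.3 and 5.1.4 place outcome assessment and e-CRF entry within the wearing period, and 5.3.1.4 collects serious events at end of use. Study end in the second row can then mean the patient's own end of participation, which makes that row coherent.

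The same reply weakens two other possible routes. The 31 March 2019 date in SAP 5 is the last visit for the study as a whole, not a promise to follow each patient until then. In SAP 9.2, "Death during prescription duration" is listed apart from death while wearing, but under a wearing-period heading. The contrast may only separate vest on from vest temporarily off.

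Most of this stands. What it does not remove is the CepiDC lookup, which by design reaches beyond last contact. Protocol 5.2.3 expects few lost patients, and one could argue that the third row overrides any CepiDC death. The documents do not say which row takes precedence.

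A reader might infer that reported mortality will be roughly doubled, or that the curve must fall to zero beyond the longest wear. Both need many deaths recorded after patients have left the study, and no visit or form provides for that. Nor is upward bias universal. Against mortality under full follow-up, the table can read low: 2.55% against 2.78% at 6 months with 0.3% per month on the device, twice that hazard afterwards and 10% of later deaths recorded.

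**Conclusion.** The rule is faulty as written: deaths have no end date, survivors do, and the SAP does not repair it. The harm is conditional. It arises only if deaths after withdrawal or last contact enter the analysis, and the bias is then upward relative to mortality on the WCD. CepiDC for lost patients is the one clearly documented route.

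The likely size is modest. At an assumed 1% per month with 2-5% lost, it is about 0.1-0.7 points at 6 months, below one standard error, though systematic rather than random. It grows with time: with 5% lost the 9-month shift was 10.96 − 8.61 = 2.35 points, against a standard error of 2.1. Full capture to the end of prescription would add about 1 point at 6 months. All these sizes rest on assumed mortality, wear and loss rates.

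Only the Kaplan-Meier and Cox survival analyses are exposed. The shock endpoints, and the survival ratio taken at end of WCD use, are not.

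**What to change.** In SAP 11, replace the protocol table for mortality with one window for everyone:

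- Count deaths up to and including the date of WCD withdrawal. Censor all other patients there, including those who die later, and list later deaths separately.
- For lost patients, apply the CepiDC result within the same window. Count a death on or before the end date, and censor a patient confirmed alive at that end date rather than at last contact. State how the end date is set when no return is recorded, for example from the last use in the device data (protocol 5.3.1.5).
- If a common later date is preferred, count deaths to that date and censor survivors at the last date known alive up to it.

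Give wear time its own rule, because there withdrawal is the event and cannot also be the censoring date.

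The cost is a few lines of SAP text and a small programming change. The CepiDC lookup and the device data are already planned, so no new data should be needed.
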